#### **6.1.1.2.5. Prevalence of adverse events of interest by week**

The number and percentage of participants who are experiencing a TEAE of interest each week (up to and including Week 12) will be tabulated by treatment group and week and overall. A separate table representing the number and percentage by severity (mild, moderate or severe) will also be produced. These tables will be produced separately for each TEAE of interest.

To calculate the percentage each week, the total number of participants who experience the TEAE of interest at any time during the respective week will be the numerator and the total number of participants who had not discontinued from IP and/or the study for the respective treatment group prior to that respective week will be the denominator (note if a participant did discontinue from IP and/or the study during that respective week they would be included in the denominator).

A figure of the overall percentage (i.e. not by severity) per week will be produced, with week on the x-axis and a separate line for each treatment group. A separate figure of the percentage per week will also be produced, with week on the x-axis and a separate line for each severity, paged by treatment group. These figures will be produced separately for each TEAE of interest.

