### **3.5. Safety Endpoints**

#### **3.5.1. Adverse Events**

An adverse event is considered treatment emergent (TEAE) relative to a given treatment if:

- the event starts during the effective duration of treatment (i.e. starting after or on the first dose but before the last dose plus lag time)

The effective duration of treatment is determined by the lag time. Any event occurring within the lag time, whether this occurs during a break in treatment or at the end of treatment, is attributed to the corresponding treatment period. The lag time is defined by the Pfizer Standard of 365 days post last dose of IP.

Adverse events occurring during the placebo run-in period (i.e. from Day -14 up to the first dose of active treatment on Day 1) will be considered non-treatment emergent.

A 3-tier approach for summarizing AEs will not be used for this study as there is a low number of subjects planned to be enrolled per treatment group, although risk differences and related summaries for AEs of interest will be presented as defined in Section 6.1.1.2.2.

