#### 6.1.1.2. Sensitivity/Supplementary Analyses

The following exploratory safety analyses will be restricted to the TEAEs of interest (as defined in Section 3.5.1.1). All sets of outputs in this section would be produced separately for "all causality" TEAEs only.

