#### 6.1.1.2.4. Incidence of first occurrence of adverse events of interest by week

The number and percentage of participants who experience the first occurrence of a TEAE of interest each week (up to and including Week 12) will be tabulated by treatment group and overall and week, where percentage will be defined in two ways. These will be included in the same table and produced separately for each TEAE of interest.

To calculate the percentage each week, the numerator will be the total number of participants with the TEAE of interest that was also their first post-dose occurrence of the event during that respective week. The two approaches for the denominator are: (1) the total overall number of evaluable participants for the respective treatment group; and (2) the total number

of participants who had not discontinued from IP and/or the study for the respective treatment group prior to that respective week (note if a participant did discontinue from IP and/or the study during that respective week they would be included in the denominator).

A figure of the percentage per week will also be produced, with week on the x-axis and a separate line for each treatment group. The percentage will represent the above definition (2) of the denominator but based on blinded data reviews this figure may be adapted or additionally produced based on definition (1). These figures will be produced separately for each TEAE of interest.

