##### **6.1.1.2.6. Time to first occurrence/recurrence of adverse events of interest**

Time to the first occurrence of TEAEs of interest will be produced using Cumulative Incidence Plots as described in Section 5.2.4. Participants who discontinue from the study, discontinue from IP or initiate glycemic rescue medication prior to the start of the TEAE of interest will be censored at the discontinuation/initiation date.

A separate plot for each TEAE will be produced separately.

The above will also be produced separately for the time to the first recurrence of the TEAEs of interest. There will be a separate line for each treatment group.

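### Weekly prevalence of nausea, vomiting and diarrhoea can count participants already off drug in the numerator after removing them from the denominator

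*SAP*

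**What the plan says.** SAP 6.1.1.2.5 tabulates, for each week up to Week 12, the number and percentage of participants with each event of interest (nausea, vomiting, diarrhoea). On the upper part of the fraction it states that "the total number of participants who experience the TEAE of interest at any time during the respective week will be the numerator". On the lower part it reads: "participants who had not discontinued from IP and/or the study for the respective treatment group prior to that respective week will be the denominator". One qualification follows: "note if a participant did discontinue from IP and/or the study during that respective week they would be included in the denominator". The same percentage carries into further outputs: "A separate table representing the number and percentage by severity (mild, moderate or severe) will also be produced", and figures are drawn overall and by severity.

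SAP 6.1.1.2.4 (first occurrence by week) counts participants with "the TEAE of interest that was also their first post-dose occurrence of the event during that respective week". It offers two denominators: (1) all evaluable participants in the group, and (2) the same not-yet-discontinued set as in 6.1.1.2.5. Definition (2) is the default for the figure.

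Three other provisions determine what happens after a participant stops drug:

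- Protocol 7.1 keeps a participant who permanently stops IP in the study on the full visit schedule.
- Protocol 8.3.1 requires active AE collection for at least 28 days after the last dose.
- SAP 3.5.1 sets the treatment-emergent window: "The lag time is defined by the Pfizer Standard of 365 days post last dose of IP".

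**The concern.** A prevalence needs its cases to come from the people in its denominator. Here the denominator is the set still on drug and in the study at the start of the week, while the numerator is anyone with the event in that week. The qualification about the week of stopping keeps the two aligned for that week only. From the following week, a participant who stopped because of nausea and is still nauseated is counted as a case but not as a person at risk. Because prevalence counts ongoing events, no new onset is needed.

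The primary objective is the tolerability of different titration schemes, and these outputs show the time course of the gastrointestinal events across arms of about 20. The excess arises only in arms and weeks with off-drug cases. An arm whose participants stop because of these events is therefore the one most open to inflation, which can distort the comparison between schemes.

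**Working it through.** **Does any other text close the gap?** None that is visible.

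- SAP 6.1.1.2 limits the type of event, not the participants: "The following exploratory safety analyses will be restricted to the TEAEs of interest".
- The two-day window in SAP 3.5.1.2 is applied in 6.1.1.2.8 and is not cited in 6.1.1.2.4 or 6.1.1.2.5. It restricts when an event starts, so an event that began on drug and persists would still count.
- The SAP states on-drug handling where it wants it. In 6.1.1.2.6, participants who "discontinue from IP or initiate glycemic rescue medication prior to the start of the TEAE of interest will be censored at the discontinuation/initiation date". Nothing equivalent appears in the two weekly sections.

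**Inputs.** SAP 2.2 gives about 20 participants per active arm, 15 on T2DM placebo and 5 on obesity placebo, 140 in all. The plan's own related figure reproduces: 140 × (1 − 0.25) = 105 completers. The documents state no weekly percentage, no rate of IP discontinuation and no count of off-drug participants with events. The values of k, e and x below are therefore assumptions.

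**Formula.** Let N be the group size, k the number who stopped IP before the week, e the on-drug cases, and x the cases among those k.

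- Plan: (e + x)/(N − k)
- Matched, on drug: e/(N − k)
- Matched, all under observation (all k still in the study): (e + x)/N

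Against the on-drug version, the excess is x/(N − k), so each off-drug case adds 100/(N − k) points:

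| Group | N | k | Points per off-drug case |
|---|---|---|---|
| Active arm | 20 | 1 | 100/19 = 5.3 |
| Active arm | 20 | 2 | 100/18 = 5.6 |
| Active arm (stress case) | 20 | 5 | 100/15 = 6.7 |
| T2DM placebo | 15 | 1 | 100/14 = 7.1 |
| Overall column | 140 | 1 to 6 | 100/139 to 100/134 = about 0.7 |

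**Example, prevalence.** N = 20, k = 1, e = 3, x = 1:

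- Plan: 4/19 = 21.1%
- On drug: 3/19 = 15.8% (plan higher by 5.3 points)
- All under observation: 4/20 = 20.0% (plan higher by 1.1 points)

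**Example, definition (2) of 6.1.1.2.4.** An event that led to the stop has already been counted correctly. The mismatch needs a first-ever onset in a week after the stopping week. With k = 1 and one on-drug and one off-drug first onset in the same week, the plan gives 2/19 = 10.5% and the matched version 1/19 = 5.3%.

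**How large might k be?** In the earlier 28-day study (Protocol 2.2.2.1), 2 of 98 participants withdrew because of adverse events: 20 × 2/98 = 0.41 per 20. If both were among the 73 on active drug (9 + 9 + 10 + 9 + 9 + 9 + 8 + 10, Protocol Table 1), it is 20 × 2/73 = 0.55 per 20. This suggests k = 0 or 1 per arm. It is only a guide: that study was shorter, used lower top doses, and counted study withdrawals rather than IP stops with continued follow-up.

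**How many rows?** The 28-day window alone spans 28/7 = 4 later weekly rows per participant, if the event lasts or recurs that long and the stop falls by Week 8.

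**The case against.** The strongest reply is that a percentage of participants is ordinarily understood to draw its cases from its denominator, so the section is under-specified rather than wrong. That is a fair account of what the author probably meant. But the section defines the denominator down to the week of stopping and defines the numerator without that limit. A programmer who follows the text produces the mismatched ratio.

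Second, the size depends on the comparator: 5.3 points in the example if the target is on-drug prevalence, but only 1.1 if it is prevalence among everyone observed. This stands, and both figures should be kept in view. The plan's value is too high against either. It also stands that the on-drug version omits persisting events in people who stopped, so the choice between the two fixes is a choice of target.

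Third, the problem may seldom arise. Protocol 7.1 describes permanent IP stops as rare. Participants who leave the study are discontinued from IP at the same time, so the 25% drop-out figure does not measure the group that stops drug and stays. Four affected rows is close to a ceiling: Arms 6 and 7 reach their top dose in Week 11, and a stop in that week leaves one row. A percentage above 100% is possible in principle but needs extreme counts; with N = 20 and k = 1, all 20 participants would need the event in the same week. All of this limits the size; none of it removes the mismatch.

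Finally, the outputs are exploratory and show counts beside percentages. This stands and sets the severity.

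**Conclusion.** The point holds and is minor. As written, 6.1.1.2.5 gives a ratio whose numerator can include people excluded from its denominator, and the error can only be upward. Definition (2) of 6.1.1.2.4 shares the fault by a narrower route. With k = 1 in an arm of 20, one off-drug case adds 5.3 points to on-drug prevalence; where nobody off drug has the event, the error is zero. These sizes rest on assumed values of k and of the case counts.

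The main TEAE tables (6.1.1.1), risk differences (6.1.1.2.2), individual profile plots (6.1.1.2.3), definition (1) and the time-to-first-event plots (6.1.1.2.6) are unaffected. No test or decision rule uses the weekly percentages.

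**What to change.** Add to 6.1.1.2.5 and to definition (2) of 6.1.1.2.4: *Only participants included in that week's denominator are counted in the numerator.* This fits the denominator already chosen and the censoring at IP discontinuation in 6.1.1.2.6.

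For prevalence only, an acceptable alternative is to use all participants still under observation in the study that week in both parts of the fraction, which keeps persisting events after a stop. The SAP should say which target is meant. Definition (1) needs no change. Applying the two-day window of 3.5.1.2 would not be enough, because it leaves ongoing events in the numerator.

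The cost is one sentence in each of two sections and a small programming filter. No new data are needed.

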##### **6.1.1.2.5.1. Adverse events of interest during Week 1**

An additional summary table (as per Section 5.2.2) of the incidence and severity of TEAEs of interest reported during the first week of treatment will be produced. In these tables, treatment groups with the same Week 1 dose (i.e. 5 mg BID or 10 mg BID) and population (i.e. T2DM or non-diabetic obesity) will be pooled and placebo will be included as two separate groups in this table along with an overall group.

##### **6.1.1.2.6. Time to first occurrence/recurrence of adverse events of interest**

Time to the first occurrence of TEAEs of interest will be produced using Cumulative Incidence Plots as described in Section 5.2.4. Participants who discontinue from the study, discontinue from IP or initiate glycemic rescue medication prior to the start of the TEAE of interest will be censored at the discontinuation/initiation date.

A separate plot for each TEAE will be produced separately.

The above will also be produced separately for the time to the first recurrence of the TEAEs of interest. There will be a separate line for each treatment group.

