#### **5.2.4. Cumulative Incidence Plots**

Cumulative Incidence Plots will be produced based on the time to the event of interest (starting from the time of start of dosing on Day 1) for each treatment group separately and will be plotted on the same graph. This will be based on plotting the cumulative incidence function (with no competing risks), which will be presented as a % on the y-axis. No statistical testing for differences between treatment groups will be considered.

Details of censoring are included in Sections 6.5.6, 6.1.1.2.6 and 6.1.1.2.7 and example SAS code is provided in Appendix 2.

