#### **6.1.1.2.7. Time to discontinuation from IP due to Gastrointestinal Disorders AEs**

Exploratory summaries on the time to discontinuation from IP (regardless of study discontinuation or continuation) due to Gastrointestinal Disorders AEs (defined as based on System Organ Class) will be produced with a Cumulative Incidence Plot as described in Section 5.2.4. Participants who discontinue will be censored at the associated discontinuation date. There will be a separate line for each treatment group.

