### Example SAS code for Cumulative Incidence Plots:

```
proc lifetest data = dataset method=km plots=cif(test) outcif=cifatrisk intervals=0 to 20 by 2;
  strata treatment;
  time day*censor(1)/eventcode=0;
run;
```

NOTE: the censor variable has a value = 1 when the related time is censored and has a value = 0 when the event of interest occurs. There should be no other values available for this censored variable in this dataset (including missing values). If required, missing observations should be removed prior to analysis.

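### Two SAP sections censor discontinuation in curves where it is the event; separately, the time-to-first-AE curves read above the observed on-treatment percentage

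*SAP*

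**What the plan says.** SAP 5.2.4 defines every cumulative incidence plot as "plotting the cumulative incidence function (with no competing risks), which will be presented as a % on the y-axis" and leaves the censoring details to sections 6.5.6, 6.1.1.2.6 and 6.1.1.2.7. The Appendix 2 code reads "time day*censor(1)/eventcode=0": status 0 is the event and status 1 is censored. Its note adds "There should be no other values available for this censored variable in this dataset".

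The three sections then say:

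- **6.5.6** (time to discontinuation from the study, and separately from IP): in both curves, those who discontinue are censored on their discontinuation date.
- **6.1.1.2.7** (time to IP discontinuation due to GI AEs): "Participants who discontinue will be censored at the associated discontinuation date".
- **6.1.1.2.6** (time to first nausea, vomiting or diarrhea, and to first recurrence): participants who leave the study, stop IP or start glycemic rescue "prior to the start of the TEAE of interest" "will be censored at the discontinuation/initiation date". No censoring time is given for participants who complete without the event.

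On status, 6.1.1.2 calls the AE-of-interest analyses exploratory, and 5.2.4 says "No statistical testing for differences between treatment groups will be considered".

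**The concern.** In 6.5.6 the rule removes the very event being plotted. A programmer who follows it with the Appendix 2 coding has no status-0 record for any discontinuer. The wording of 6.1.1.2.7 has the same defect unless one reads into it a restriction to other reasons for stopping. These curves show how long participants stay on each titration scheme, which bears directly on tolerability.

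In 6.1.1.2.6 the rule is workable, but it produces a quantity that the axis label does not describe. With two states the estimate is one minus Kaplan-Meier, which treats each person who stops IP, leaves or is rescued as still facing the AE risk of those who continue. Someone who stops for nausea before any vomiting is handled this way on the vomiting curve. A reader who takes the percentage as the share of the arm that had the AE on treatment will read too high.

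The curve will also differ from the plan's own tables. SAP 3.5.1 counts treatment-emergent AEs up to 365 days after last dose, and 3.5.1.2 counts onsets up to two days after it. Glycemic rescue does not stop nausea from being observed, and the main AE analysis in 6.1.1.1 has no rescue rule.

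**Working it through.** **Planning figure.** Protocol 9.2 gives 140 randomized, 25% drop-out and 105 completers. Check: 105/(1 - 0.25) = 140, and the arms sum to 5×20 + 15 + 20 + 5 = 140. It reproduces. The documents give no figure for the curves themselves.

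**Discontinuation curves.** At 25% drop-out, 140 - 105 = 35 participants discontinue from the study. With all 35 coded 0, the overall curve ends at 35/140 = 25%. Under the rule in 6.5.6 all 35 are coded 1. Nobody else has an event, so no status 0 exists and the curve is flat at 0% or empty. In 6.1.1.2.7 the plain wording gives the same result. If the sentence is instead read as covering only stops for other reasons, the curve exists, but as one minus Kaplan-Meier with those stops treated as non-informative.

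**Time-to-first-AE curves.** Inputs:

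- Illustrative values *p* for one minus Kaplan-Meier at week 12: nausea 49.0%, vomiting 26.5%, diarrhea 24.5%. These are the frequencies in the earlier 28-day study (Protocol 2.2.2.1), borrowed as assumptions.
- Proportion *d* stopping by week 12: 25%, range 10-50%. This is an assumption, because 25% is study drop-out and the IP-stop rate is not stated.
- Independent, constant hazards.

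The on-treatment cumulative incidence (Aalen-Johansen, with stopping as a competing event) is

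AJ = [ln(1-p) / (ln(1-p) + ln(1-d))] × [1 - (1-p)(1-d)].

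For nausea at *d* = 0.25: 0.673/(0.673 + 0.288) × (1 - 0.51×0.75) = 0.7007 × 0.6175 = 0.433.

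| AE | 1-KM | AJ, 25% stop | Gap (points) | Participants per 20 | Gap at 10-50% stopping (points) |
|---|---|---|---|---|---|
| Nausea | 49.0% | 43.3% | 5.7 | 1.1 | 2.2-12.3 |
| Vomiting | 26.5% | 23.2% | 3.3 | 0.7 | 1.3-7.0 |
| Diarrhea | 24.5% | 21.4% | 3.1 | 0.6 | 1.2-6.5 |

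**Dependence on timing.** Take an arm of 20 with 9 first AEs and 5 people who stop without having had the AE. The observed share is 9/20 = 45%. One minus Kaplan-Meier is 45.0% if all the stops come after the nine AEs, 52.7% in one interleaved order, and 9/15 = 60.0% if all the stops come first. It is never below the observed share.

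**Dependence on the target.** Suppose AEs after stopping were also counted, with the nausea hazard multiplied by *k* after the stop (25% stopping). The risk is then 43.3% for *k* = 0, 46.5% for 0.5, 49.0% for 1 and 52.6% for 2, against a curve at 49.0%. The curve is too high if *k* < 1 and too low if *k* > 1.

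Now suppose half the participants have weekly AE and stopping hazards of 0.03 and 0.012, and the other half four times both. The risk with no stopping is 1 - 0.5×(e^-0.36 + e^-1.44) = 53.3%. One minus Kaplan-Meier gives 51.0%, and on-treatment incidence is 45.1%. Here the curve is above one target and below the other.

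**The case against.** The strongest reply concerns the AE curves. Censoring at IP stop or rescue can be read as aiming at the risk had everyone stayed on IP without rescue, much like the strategy for the secondary estimands. For that target one minus Kaplan-Meier is unbiased under independent censoring. This stands. A reader might infer that the curves simply overstate AE risk; that holds only against the observed on-treatment share. The SAP defines no estimand for AEs, so the target has to be stated.

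Nor is tolerability drop-out lost wholesale. Only exits before the AE in question are censored, so someone who stops because of nausea is already an event on the nausea curve. Protocol 7.1 expects permanent IP stops to be rare, and 2 of 98 participants in the earlier study withdrew for AEs.

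Larger gaps can be produced. A true 27% vomiting with 40% stopping first would display as 36%, 9 points too high. But 40% stopping before vomiting exceeds the plan's total drop-out of 25%. A reader might also infer that differences between arms are partly artifacts of censoring. That is possible if stopping rates differ, but the documents give no arm-specific rates.

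The observed quantities are planned elsewhere: crude incidence (6.1.1.1), incidence with confidence intervals and risk differences (6.1.1.2.1 and 6.1.1.2.2), weekly first occurrence over all evaluable participants (6.1.1.2.4), and the two-day interval (6.1.1.2.8). This limits the harm.

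On the discontinuation curves, the reply is that the intent is obvious and 6.1.1.2.7 can be read charitably. For 6.5.6 no such reading is available, because the sentence names exactly the people whose discontinuation is being timed.

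**Conclusion.** The censoring rule in 6.5.6 is wrong as written, and so is 6.1.1.2.7 on its plain wording: followed literally, they give curves with no events. This rests on the text and the Appendix 2 coding alone, with no assumption about rates.

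The time-to-first-AE curves are a secondary matter and a cheap improvement. At 25% stopping by week 12 they read about 6 points (nausea) or 3 points (vomiting, diarrhea) above the observed on-treatment share, roughly one participant or fewer in an arm of 20. Over 10-50% stopping the range is about 1 to 12 points. These figures assume constant independent hazards, event rates from a shorter study, and a stopping rate borrowed from study drop-out. The gap shrinks to zero if the AEs all precede the stops.

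The documents do not support reading this as a flaw in the primary analysis: that analysis is crude incidence and severity, and these curves are exploratory and untested.

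**What to change.** **Discontinuation curves.**

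- 6.5.6: code study (or IP) discontinuation as status 0. Censor non-discontinuers at end of observation (or end of treatment).
- 6.1.1.2.7: code IP discontinuation due to GI AEs as status 0 and IP discontinuation for any other reason as a competing event with a third status value. Censor completers at end of treatment.

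**Time-to-first-AE curves (5.2.4, 6.1.1.2.6).** State the target, then choose one of two valid repairs:

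- For on-treatment incidence, code IP or study discontinuation as a competing event (Aalen-Johansen) and count onsets up to two days after last dose, as in 3.5.1.2.
- Otherwise keep counting AEs after IP stop and censor only at end of observation. Participants who stop IP remain in the study (Protocol 7.1), so these AEs are observable, and the curve would then follow the treatment-emergent definition in 3.5.1.

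In either case, do not censor GI AEs at glycemic rescue, give a censoring time for completers without the event, and label the axis with the quantity plotted. Amend the Appendix 2 note, which at present forbids a third status value.

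**Cost.** SAP wording, one status code and re-derived event and censoring times; no new data. The downside of the competing-event version is that each AE curve must be read beside the discontinuation curve, since frequent early stopping lowers it.
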